4.3.1.2 Macugen for Treatment of Diabetic Macular Edema (DME)

EOP1002 was an open label study of intravitreal injections of 3 mg pegaptanib sodium/eye every 6 weeks for up to 36 weeks in ten (10) patients with diabetic macular edema (DME). No dose limiting toxicities were reported and there were no premature withdrawals from the EOP1002 study due to treatment-related AEs. A total of 69 AEs were reported, 29 of which were considered treatment related. Treatment-related AEs were mostly (28/29 reports) due to the injection procedure. There were 5 SAEs experienced by two subjects, with one subject dying 26 days after the last injection of study treatment due to multisystem organ failure and pneumonia. None of the SAEs was considered treatment-related.

A phase 2 dose-ranging study, EOP1005 was conducted to evaluate safety and efficacy of Macugen[®] (pegaptanib sodium injection) in the treatment of diabetic macular edema (DME) [11]. This was a randomized, double-masked, multicenter, dose-ranging, controlled trial. Intravitreal pegaptanib sodium (0.3 mg, 1 mg, 3 mg) or sham injections were given at study entry, week 6, and week 12 with additional injections and/or focal photocoagulation as needed for another 18 weeks. Final assessments were conducted at week 36. A total of 172 subjects were enrolled. Median VA was better at week 36 with pegaptanib sodium 0.3 mg (20/50), as compared with sham (20/63) ($P = 0.04$). A larger proportion of those receiving 0.3 mg gained VAs of ≥ 10 letters (approximately 2 lines) (34% vs. 10%, $P = 0.003$) and ≥ 15 letters (18% vs. 7%, $P = 0.12$). The results of this exploratory Phase 2 study did not identify any safety concerns for the treatment of patients with DME. Pegaptanib sodium was generally well tolerated. The safety profile in this study appears similar to that established in the

age-related macular degeneration (AMD) indication, with additional findings consistent with what would be anticipated in a diabetic population.

A subsequent phase 2/3 study [EOP1013] was conducted to confirm the safety and compare the efficacy of intravitreal Macugen® (pegaptanib sodium injection) 0.3 mg versus sham injections in subjects with DME [12]. This was a 2 year study, with 260 (pegaptanib, n = 133; sham, n = 127) and 207 (pegaptanib, n = 107; sham, n = 100) subjects included in years 1 and 2 intent-to-treat analyses, respectively. Change in mean visual acuity from baseline for pegaptanib sodium was superior to sham injection ($P < 0.05$) at weeks 6, 24, 30, 36, 42, 54, 78, 84, 90, 96, and 102. Additionally pegaptanib-treated subjects gained 6.1 letters on average at week 102 compared to 1.3 letters for sham injection. Pegaptanib was well tolerated, with frequencies of adverse events, treatment-related adverse events, and serious adverse events comparable in both treatment groups.

The analysis of VA and fluorescein angiograms in the EOP1006 study showed a pattern of greater vision loss during the first year of the study followed by a degree of stabilization. Macugen® was generally well tolerated, with AEs predominantly ocular in nature, mild, and predictable. The most frequently occurring ophthalmic adverse events during Years 2 and 3 were punctate keratitis, vitreous floaters, and eye pain. Four subjects experienced ophthalmic SAEs during Years 2 and 3, including 3 reports of endophthalmitis (related to the injection procedure). No generalized systemic safety concerns were observed, as most events other than eye disorders were infrequent and of the types often seen in an elderly population.

4.3.1.3 Macugen for Treatment of Central Retinal Vein Occlusion (CRVO)

The phase 2 study, EOP 1011 assessed the safety and efficacy of intravitreal pegaptanib sodium for the treatment of macular edema following central retinal vein occlusion (CRVO). This was a dose-ranging, double-masked, multicenter trial including subjects with CRVO for 6 month or less duration randomly assigned (1:1:1) to receive pegaptanib sodium or sham injections every 6 weeks for 24 weeks (0.3 mg and 1 mg, n=33; sham, n=32). In the primary analysis at week 30, 12 of 33 (36%) subjects treated with 0.3 mg of pegaptanib sodium and 13 of 33 (39%) treated with 1 mg of pegaptanib sodium gained 15 or more letters from baseline vs. 9 of 32 (28%) sham treated subjects ($P=.48$ for 0.3 mg and $P=.35$ for 1 mg of pegaptanib sodium vs. sham). In secondary analyses, subjects treated with pegaptanib sodium were less likely to lose 15 or more letters (9% and 6%; 0.3-mg and 1-mg pegaptanib sodium groups, respectively) compared with sham-treated eyes (31%; $P=.03$ for 0.3 mg and $P=.01$ for 1 mg of pegaptanib sodium vs. sham). Pegaptanib sodium was generally well tolerated. AEs were predominantly ocular in nature, mild and predictable. No new safety concerns were detected [13].

4.3.1.4 Macugen for Treatment of Branched Retinal Vein Occlusion (BRVO)

Twenty subjects from three clinical practices in the US with BRVO of 1-6 months duration and central foveal thickness of 250 μm or more were included in this study. Subjects were randomized 3:1 to intravitreal injections of Macugen (pegaptanib sodium) 0.3 or 1.0 mg at baseline and at weeks 6 and 12 with subsequent injections at 6-week intervals at investigator discretion until week 48. Fifteen (15) subjects received 0.3 mg Macugen and Five (5) subjects received 1.0 mg Macugen. The majority of subjects completed the 54-week follow-up visit, and results were similar for both Macugen doses. VA response was rapid after the first dose, with mean BCVA improvement of 11 ± 7 letters at 1 week from baseline. There was one retinal detachment and no cases of endophthalmitis [14].

4.4 Corneal Endothelium and Clinical Specular Microscopy

A specular microscope will be used to assess adverse effects of the corneal endothelium. Results will be compared individually for central cell density and cell characteristics changes (polymegathism and polymorphism) occurring from baseline.

The corneal endothelium is the posterior layer of the cornea consisting of a single layer of cells, about 5 μm thick, bound together and predominantly hexagonal in shape. The posterior border is in direct contact with the aqueous humour while the anterior border is in contact with Descemet's membrane. The endothelium is the structure responsible for the relative dehydration of the corneal stroma. The endothelium receives most of its energy from the oxidative breakdown of carbohydrates via the Krebs cycle. In the normal adult eye the cell density varies from around 3000 cells/ mm^2 in the centre of the cornea to about 2000 cells/ mm^2 in the periphery. With age, disease or trauma the density of cells decreases but with disease or trauma this reduction may affect corneal transparency, as some fluid then leaks into the cornea.

The corneal endothelial cells do not replicate in general. When destroyed by disease or surgery, the remaining cells enlarge and spread out to cover the posterior corneal surface, thus decreasing the cell density (cell count). Corneas with extremely low endothelial cell densities can no longer maintain a dehydrated state. The corneas may decompensate, swell, and become cloudy over time, with an associated loss of visual acuity. The specular microscope provides a magnified view of a small area of corneal endothelial cells to measure and record endothelial cell counts of the cornea.

5.0 STUDY OBJECTIVE

5.1 Objective

The objective of this study will be to assess the effect of intravitreal injections of Macugen[®] (pegaptanib sodium injection) administered every 6 weeks for 48 weeks on the corneal endothelium.

6.0 INVESTIGATIONAL PLAN

6.1 Study Design

This will be a Phase IV, open label, multi-center study. Subjects will receive intravitreal injections of Macugen[®] (pegaptanib sodium) every 6 weeks for 48 weeks. Additional therapy may be employed at the Investigator's discretion for circumstances judged to be deterioration. The Investigator will decide which treatment to provide as additional therapy. Macugen[®] (pegaptanib sodium injection) injections should remain on the 6-week schedule defined by the protocol even if an additional therapy is given.

6.2 Rationale

Due to the lack of information generated in the pivotal phase III trials assessing potential effects of intravitreal injections of Macugen[®] on the corneal endothelium, the FDA requested clinical information from a 1-year (minimum) clinical study to support that there are no adverse effects on the corneal endothelium following intravitreal injections of Macugen[®].

6.3 Eligibility Criteria

6.3.1 Inclusion Criteria

6.3.1.1 Ophthalmic Criteria

6.3.1.1.1 Subjects of either gender aged ≥ 50 years diagnosed with subfoveal neovascular Age-Related Macular Degeneration (AMD), Diabetic Macular Edema (DME) or Retinal Vein Occlusion (RVO)

6.3.1.1.2 Best corrected visual acuity in the study eye between 85 and 20 ETDRS letters or between 20/20 and 20/400 using a Snellen chart

6.3.1.2 General Criteria

6.3.1.2.1 Women must be using **two forms** of effective contraception, be post-menopausal for at least 12 months prior to study entry, or surgically sterile; **if of child-bearing potential**, a urine pregnancy test must be performed within 7 days prior to the first injection with a negative result. If the test is positive, a serum test must be done to confirm. The **two forms** of effective contraception must be implemented during the study and for at least 60 days following the last dose of test medication.

6.3.1.2.2 Provide written informed consent.

6.3.1.2.3 Ability to return for all study visits.

6.3.2 Exclusion Criteria

Subjects will not be eligible for the study if subjects cannot attend all study-required visits, or if any of the following criteria are present

Valeant Pharmaceuticals

- 6.3.2.1 Unilateral ocular blunt trauma within one year of enrollment and no greater than 5% difference in central endothelial cell density between the 2 eyes
- 6.3.2.2 intraocular surgery (cataract surgery and surgery for glaucoma without tube shunt or mini-shunt) within one year of enrollment
- 6.3.2.3 Anterior segment laser surgery (laser trabeculoplasty) performed within one year of enrollment
- 6.3.2.4 Glaucoma tube-shunt surgery
- 6.3.2.5 Previous history of corneal transplant in the study or non-study eye.
- 6.3.2.6 Presence of vitreous macular traction
- 6.3.2.7 Previous therapeutic radiation in the region of the study eye.
- 6.3.2.8 Any treatment with an investigational agent in the past 30 days for any condition.
- 6.3.2.9 Known serious allergies to the components of pegaptanib sodium formulation
- 6.3.2.10 Any of the following underlying diseases including:
 - 6.3.2.10.1 History or evidence of severe cardiac disease (e.g., NYHA Functional Class III or IV - see [Appendix 2](#)), clinical or medical history of unstable angina, acute coronary syndrome, myocardial infarction or revascularization within 6 months, ventricular tachyarrhythmias requiring ongoing treatment.
 - 6.3.2.10.2 History or evidence of clinically significant peripheral vascular disease, such as intermittent claudication or prior amputation.
 - 6.3.2.10.3 History or evidence of clinically significant impaired renal or hepatic function
 - 6.3.2.10.4 Stroke (within 12 months of study entry).
 - 6.3.2.10.5 Any major surgical procedure within one month of study entry.
- 6.3.2.11 Significant media opacities, including cataract, which might interfere with visual acuity, or assessment of toxicity. Subjects should not be entered if there is likelihood that they will require cataract or glaucoma surgery in either eye during the study treatment and follow-up period.

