Test Product, Dose, Formulation and Mode of Administration:	
Test Product: Macugen® (pegaptanib sodium injection) Administration: intravitreal injection Dose: All subjects will receive intravitreal injections of 0.3 mg/eye pegaptanib sodium every 6 weeks for 48 weeks.
 
Other available therapy of the Investigator's choice may be employed at the Investigator's discretion for circumstances judged to be clinical deterioration, such as but not restricted to: ≥ 2 line vision loss; retinal thickness at center point $\geq 300\mu\text{m}$; an increase of retinal thickness at center point $\geq 100\mu\text{m}$ from baseline visit.

Corneal Specular Microscopy	
Specular microscopy assessments of the corneal endothelium will be completed and compared individually for central cell density and cell characteristics changes (polymegathism and polymorphism) occurring from baseline. All 10 targeted clinical sites will perform corneal specular microscopy assessments on a total of approximately 125 enrolled subjects. Both contact and non-contact microscopes are permitted, but consistency throughout the entire study is required (same method must be used for each subject throughout the study). Corneal specular microscopy examinations must be performed at Baseline and at Weeks 24 and 54 or early withdrawal. All examinations that are collected for the study must be sent to Central Image Analysis Reading Center (CIARC, Cleveland, OH) within 3 days of collection. For complete procedures for specular microscopy of the corneal endothelium and data transfer, please refer to the Corneal Specular Microscopy Instruction Manual.

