8.0 STUDY CONDUCT

8.1 Study Evaluations

Written informed consent must be obtained before any of the Baseline procedures listed below are performed. An explanation of the study and discussion of the possible risks and discomforts will be given by the Investigator. Only those subjects who fulfill all eligibility criteria will be entered into the study.

The following assessments will be performed at Baseline and during the treatment and follow-up periods. All visits for injections must occur within +/- 14 days of the schedule.

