8.2 Protocol Compliance and Violations

The protocol must be read thoroughly and the instructions should be followed exactly. Either the Sponsor or the Investigator without agreement by both parties will not implement modifications to the study protocol. However, the Investigator may implement a deviation from, or a change of, the protocol to eliminate an immediate hazard(s) to the study subjects without prior IRB/Sponsor approval/favorable opinion. As soon as

possible, the implemented deviation or change, the reasons for it and, if appropriate, the proposed protocol amendment should be submitted to the IRB/Sponsor. Significant protocol deviations or violations may require that the subject be withdrawn from the study. The Investigator is responsible for notifying the IRB of all protocol deviations or violations.

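### Exclusion 6.3.2.1 does not work as worded: neither reading of its 5% density limb gives a usable rule, and the intended rule is not stated

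*Combined protocol and SAP*

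**What the plan says.** Section 6.3.2 makes a subject ineligible "if any of the following criteria are present". The first item, 6.3.2.1, is "Unilateral ocular blunt trauma within one year of enrollment and no greater than 5% difference in central endothelial cell density between the 2 eyes". The exclusion list in the Section 2.0 synopsis carries the same sentence, so neither copy corrects the other.

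Three other places bear on how it should be read:

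- Section 4.4, on the biology: "With age, disease or trauma the density of cells decreases".
- Section 8.1, on entry: "Only those subjects who fulfill all eligibility criteria will be entered into the study".
- Section 8.2, on compliance: "The protocol must be read thoroughly and the instructions should be followed exactly".

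The next two items, 6.3.2.2 (intraocular surgery) and 6.3.2.3 ("Anterior segment laser surgery (laser trabeculoplasty) performed within one year of enrollment"), use the same one-year window and attach no density condition. No other listed exclusion names ocular trauma or a difference in density between the eyes.

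**The concern.** The item joins an event that could damage the endothelium to a condition describing eyes that look alike, and places the pair in a list of reasons to refuse entry. A site that applies it exactly would turn away a recently injured subject whose eyes match. On this item it would accept one whose eyes differ, who is the subject more likely to have lost cells.

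The item concerns the variable that the study measures. The corneal endpoint (Sections 2.0 and 9.2) is loss of endothelial cell density from baseline, and the purpose (Section 6.2) is to support an absence of adverse effects on the endothelium. There is no control arm. If an injured study eye went on losing cells after baseline because of the injury, the study could not separate that loss from an effect of the drug or the injection.

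**Working it through.** **Inputs.** The sentence at 6.3.2.1 and its copy in Section 2.0; the operator in Section 6.3.2; the statement on trauma in Section 4.4; and the central density of about 3000 cells/mm² that Section 4.4 gives for a normal adult eye. The documents give no trauma frequency, no spread of inter-eye differences and no rate of cell loss after trauma. There is no plan figure to reproduce.

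**Step 1: what each reading does.** Let T be recent unilateral blunt trauma and D the inter-eye difference in central density.

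- Literal reading (one joint condition): exclude if T and D ≤ 5%.
- Two separate exclusions: exclude if T, or if D ≤ 5%.

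Three rules that the sponsor might have meant are set beside them:

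- Limb reversed: exclude if T and D > 5%.
- Misplaced entry requirement: exclude if T, and separately require D ≤ 5%.
- No density limb: exclude if T.

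| Subject | Literal | Two exclusions | Limb reversed | Entry requirement | No density limb |
|---|---|---|---|---|---|
| Trauma, D ≤ 5% | out | out | in | out | out |
| Trauma, D > 5% | **in** | out | out | out | out |
| No trauma, D ≤ 5% | in | **out** | in | in | in |
| No trauma, D > 5% | in | in | in | out | in |

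These are logical combinations, not counts of subjects, and *in* means only that this item does not exclude.

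**Step 2: illustration.** Take D = 100 × |a − b| / max(a, b), with the better eye at 3000. The protocol names no denominator, so this form is an assumption. It matters only close to 5% and does not affect the direction of the rule.

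- Other eye 2900: 100/3000 = 3.3%.
- Other eye 2850: 150/3000 = 5.0%.
- Other eye 2800: 200/3000 = 6.7%.
- Other eye 2400: 600/3000 = 20%.

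With recent unilateral trauma, the literal reading excludes the first two and passes the last two. Without trauma, the two-exclusion reading bars the first two and admits the last two.

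**Step 3: set this against Section 4.4.** If trauma lowers density, a wide gap after a one-sided injury is the expected sign of damage. The literal reading passes the subject with a 20% gap and refuses the one with a 3.3% gap. The two-exclusion reading refuses an uninjured subject with matching eyes, for whom the documents give no ground for exclusion. Each bold cell is therefore wrong on the protocol's own account, without reference to the candidate repairs.

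**Step 4: what the documents settle.** All three candidate rules exclude trauma with D > 5% and admit uninjured subjects with D ≤ 5%. They disagree on the other two rows, and nothing in the documents decides those rows.

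**Step 5: route to the endpoint.** A difference already present at baseline is subtracted out of a change from baseline. Bias in the study-eye result needs both an injured study eye and loss that continues after baseline. If the fellow eye was injured, or if the loss was complete by baseline, there is none.

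**The case against.** The strongest case against acting is that this is a drafting slip that sites will see through, with little consequence. The general compliance sentence in Section 8.2 does not show how any site reads this item. A traumatised subject may still be refused under another item, such as 6.3.2.11: "Significant media opacities, including cataract, which might interfere with visual acuity, or assessment of toxicity". The change-from-baseline endpoint removes asymmetry that is stable. Ophthalmic history is taken and both eyes are imaged, so affected subjects should be largely identifiable afterwards. All of this stands, and it limits the size of the point. It does not give a reading under which the sentence works.

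A reader might go further and infer that the limb is simply the wrong way round and that more than 5% was meant. Section 4.4 makes that plausible, but the documents do not establish it. The phrase would have the right direction if it were an entry requirement for symmetric eyes that ended up in the wrong list. The two explanations lead to different rules, as the last two rows of trauma and non-trauma disagreement in the table show. The public text also opens partway through a list containing exclusion items, and the page before it is not available, so an explanation there cannot be ruled out.

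A reader might also infer that the results will be biased. The documents do not support that either: they give no number of affected subjects and no rate of later loss, which may be zero.

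**Conclusion.** The point holds as a defect in a stated eligibility rule. Exclusion 6.3.2.1 gives a wrong result if followed exactly, under either way of reading its conjunction, and no other section corrects it. That conclusion rests on the text and on the Section 4.4 statement that trauma lowers density. What the sponsor intended remains unknown.

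The effect on the results cannot be computed and is probably small, for the reasons in Step 5. The sentence should still be corrected, because it governs entry to an uncontrolled study of endothelial safety and the correction is cheap. It is not a reason to doubt the study as a whole.

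**What to change.** The sponsor should state the intended rule and word it identically in Sections 2.0 and 6.3.2.1. Whatever rule is chosen, it should exclude recent unilateral trauma with a difference above 5% and should not exclude uninjured subjects whose eyes match.

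The simplest wording deletes the 5% limb, so that recent unilateral blunt trauma is excluded outright, in line with the neighbouring surgery and laser items. This needs no density value to decide eligibility, but it gives up any symmetry condition that the sponsor wanted. Keeping such a condition as a separate entry requirement is possible, and may add screen failures whose number cannot be computed from the documents.

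The edit is one sentence in two places. Because it changes eligibility, it also needs agreement between sponsor and investigator (Section 8.2) and an amendment with ethics approval where required (Section 12.1).

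If subjects have already entered under the present text, the final data analysis plan, which Section 10.2.1 schedules before database lock, should list those with recent unilateral trauma and add a sensitivity analysis without them. The added cost is one listing and one repeat of the density summary.

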
Exclusion Criteria
	
 • Unilateral ocular blunt trauma within one year of enrollment and no greater than 5% difference in central endothelial cell density between the 2 eyes. • Intraocular surgery (cataract surgery and surgery for glaucoma without tube shunt or mini-shunt) within one year of enrollment • Anterior segment laser surgery (laser trabeculoplasty) performed within one year of enrollment • Glaucoma tube-shunt surgery • Previous history of corneal transplant in the study or non-study eye. • Presence of vitreous macular traction • Previous therapeutic radiation in the region of the study eye. • Any treatment with an investigational agent in the past 30 days for any condition. • Known serious allergies to the components of pegaptanib sodium (pegaptanib sodium injection) formulation • Any of the following underlying diseases including: 
 ○ History or evidence of severe cardiac disease (e.g., NYHA Functional Class III or IV - see Appendix 2, clinical or medical history of unstable angina, acute coronary syndrome, myocardial infarction or revascularization within 6 months, ventricular tachyarrhythmias requiring ongoing treatment. ○ History or evidence of clinically significant peripheral vascular disease, such as intermittent claudication or prior amputation. ○ History or evidence of clinically significant impaired renal or hepatic function ○ Stroke (within 12 months of study entry). ○ Any major surgical procedure within one month of study entry. • Significant media opacities, including cataract, which might interfere with visual acuity, or assessment of toxicity. Subjects should not be entered if there is likelihood that they will require cataract or glaucoma surgery in either eye during the study treatment and follow-up period.

Statistics	Descriptive statistics will be provided to summarize baseline and on-study measures, including demographic information, treatment administration, study outcomes and protocol deviations.
Safety	All adverse events spontaneously reported, elicited or observed by the Investigators, will be recorded.

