7.0 STUDY MEDICATION

7.1 Investigational Drug Supply

Bausch Health will provide study drug to the sites. The drug provided will be specifically labeled as clinical trial materials for this study, utilizing a label on both the primary foil pouch and the carton. The carton will be closed and secured with tamper evident tape.

Pegaptanib sodium drug substance is a pegylated (40 kDa branched PEG molecule consisting of two 20 kDa PEG arms) anti-VEGF aptamer. It is formulated in phosphate

buffered saline at pH 6-7. Sodium hydroxide or hydrochloric acid may be added for pH adjustment.

The drug product is supplied in a sterile foil pouch as a single-use glass pre-filled syringe. After proper preparation, the syringe will contain 0.3mg of Macugen[®] in a nominal 90µL deliverable volume pack. A sterile packaged BD[®] single use 30G X ½” Precision Glide[®] Luer Lok[®] needle is supplied in a separate pouch. The foil pouch and needle are packaged together in a carton. For a full description of the drug product, please review the package insert located in [Appendix 1](#).

Active Ingredient:	Pegaptanib Sodium Injection formulated as: 3.47mg/mL solution to deliver a dose of 0.3mg pegaptanib sodium injection
Excipients:	Sodium Chloride, USP Sodium Phosphate Monobasic, Monohydrate, USP Sodium Phosphate Dibasic, Heptahydrate, USP Sodium Hydroxide, USP (as needed) Hydrochloric acid, USP (as needed) Water for injection, USP

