7.2 Dose and Administration

7.2.1 Preparation

The drug product, pegaptanib sodium, is a ready-to-use sterile solution provided in a single-use glass syringe. Ensure that the drug to be administered is labeled specifically for this study. Preparation of the syringe for drug administration includes the following steps (see [Appendix 1](#) for more details):

1. Remove the syringe from the plastic clip.
2. Twist off cap.
3. Attach the sterile administration needle (included) to the syringe by screwing it into the syringe tip. Another sterile administration needle may be used in lieu of the one included. Remove the plastic needle shield from the needle.
4. Holding the syringe with the needle pointing up, check the syringe for bubbles. If there are bubbles, gently tap the syringe with your finger until the bubbles rise to the top of the syringe. SLOWLY depress the plunger rod to eliminate all the bubbles and to expel the excess drug so that the top edge of the 3rd rib on the plunger aligns with the pre-printed black dosing line.
5. Inject the entire contents of the syringe.

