7.2.2 Treatment Regimen and Duration

Pegaptanib sodium will be administered as 90µl (nominal delivered volume) intravitreal injections every 6 weeks from Day 0 to Week 48 as described in Section 3, Study Flow Chart.

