7.2.3 Administration of Study Drug and Controls

The method for intravitreal administration of pegaptanib sodium is described in [Appendix 1](#).

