4 CONTRAINDICATIONS
4.1 Ocular or Periorbital Infections
MACUGEN is contraindicated in patients with ocular or periorbital infections.

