4.2 Hypersensitivity
MACUGEN is contraindicated in patients with known hypersensitivity to pegaptanib sodium or any other component in this product.

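### The exclusion criteria are looser than the contraindications in the label attached as Appendix 1: only serious allergy is excluded, and ocular or periorbital infection is not mentioned

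*Combined protocol and SAP*

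**What the plan says.** Section 6.3.2.9 excludes "Known serious allergies to the components of pegaptanib sodium formulation". The synopsis (section 2.0) has the same criterion: "Known serious allergies to the components of pegaptanib sodium (pegaptanib sodium injection) formulation". Neither list has an item on infection of the eye or the surrounding tissue. Under section 8.1, entry depends on meeting all the eligibility criteria.

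The prescribing information in Appendix 1 states in its section 4.1 that "MACUGEN is contraindicated in patients with ocular or periorbital infections", and in its section 4.2 that "MACUGEN is contraindicated in patients with known hypersensitivity to pegaptanib sodium or any other component in this product".

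The protocol body sends the reader to Appendix 1 in three places:
- Section 7.1, for the product: "For a full description of the drug product, please review the package insert located in" that appendix.
- Section 7.2.1, for syringe preparation: "Preparation of the syringe for drug administration includes the following steps", with the appendix cited for more detail.
- Section 7.2.3, for the injection: "The method for intravitreal administration of pegaptanib sodium is described in" the appendix.

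Section 7.2.2 sets the regimen as "intravitreal injections every 6 weeks from Day 0 to Week 48" and attaches no condition for withholding or deferring a dose.

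**The concern.** The entry rules and the attached label answer the same question differently. A subject with a known but non-serious reaction to pegaptanib, or with an active periorbital infection on Day 0, passes sections 6.3.1 and 6.3.2 as written, yet the label contraindicates treatment.

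What is at stake is the safety of individual subjects and the clarity of the entry rule. The study gives an intravitreal injection up to nine times, so the infection question comes up again at each later visit. Nothing in the estimation of endothelial cell loss depends on the answer.

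**Working it through.** No formula applies, and the plan states no figure to reproduce. The check sets the two exclusion lists against the two label contraindications.

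**Step 1. Count the criteria.** Section 6.3.2 runs from 6.3.2.1 to 6.3.2.11, which is 11 criteria. The synopsis list also has 11 bullets.

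**Step 2. Compare.**

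| Label (Appendix 1) | Section 6.3.2 | Synopsis | Carried over? |
|---|---|---|---|
| 4.1: ocular or periorbital infection | 0 of 11 criteria | 0 of 11 bullets | No |
| 4.2: known hypersensitivity, no severity threshold | 6.3.2.9, limited to serious allergy | Same limit | In part |

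So 2 of 2 contraindications are not fully carried over. The severity limit appears in both lists, so it is not a slip in one place.

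**Step 3. Look for a route by which the label becomes an entry rule.** The three pointers to Appendix 1 concern product description, preparation and administration. None concerns eligibility, and no criterion in 6.3.1 or 6.3.2 cites the appendix.

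**Step 4. Look for procedures that would catch such a subject.**
- *Before the first injection.* Section 8.1.1 requires medical and ophthalmologic history and a review of concomitant medication. Section 8.1.2 repeats the medication review on Day 0. A known allergy or a treated eye infection would ordinarily surface here. Neither list names an infection check or says what follows if one is found.
- *At each injection.* Label 2.4, reached through section 7.2.3, asks for the hypersensitivity history to be evaluated before the procedure. As reproduced, it does not say that the dose is withheld, and it contains no pre-injection infection check.
- *At Weeks 6 to 48.* Section 11.1 requires each treated eye to be examined for adverse events at all visits. This covers 8 of the 9 injections (Day 0 plus 8 later visits = 9). It does not say that the examination comes before dosing, and on Day 0 the eye has not yet been treated.
- *After injection.* Label 5.1 asks for monitoring during the following week, which cannot serve as an entry check.
- *Discretion.* Section 8.2 allows a deviation to remove an immediate hazard, section 8.3 allows withdrawal, and the 14-day window either side of each injection visit leaves room for delay. These permit the right action but do not require it.

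**Step 5. Size.** The documents give no rate of active infection, or of known non-serious hypersensitivity, at an injection visit. The risk cannot be quantified from them.

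**The case against.** The strongest reply is that exclusion criteria say who may not enter; they do not order anyone to dose a contraindicated patient. Appendix 1 is part of the protocol, every site holds it, and section 13.1 also requires the current insert on file. With the history, the medication review and label 2.4, a competent injector would rarely go wrong. The allergy gap is also narrow: the excipients listed in section 7.1 are simple salts, pH adjusters and water, so the word serious matters mainly for mild reactions to pegaptanib itself, including its polyethylene glycol part. For infection, the clearest gap is Day 0, because section 11.1 covers treated eyes afterwards.

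Most of this stands, and it limits the size of the point. It does not remove it. Section 8.1 ties entry to the listed criteria, and those are looser than the label. Where the label asks for the hypersensitivity history, the protocol gives that history a narrower consequence than the label does.

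Two stronger readings are tempting, and the documents support neither. A reader might infer that some sites would follow section 6.3.2 and others Appendix 1, so that practice would split across the study. All sites hold both texts, and nothing shows that they would act differently. A reader might also infer that the protocol has no safeguard against dosing such a subject. Step 4 above shows several; what is missing is a rule.

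**Conclusion.** The point holds as a minor patient-safety inconsistency. Both label contraindications are incompletely reflected in both exclusion lists, so a contraindicated subject can satisfy every written entry criterion. Dosing such a subject is unlikely in practice.

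The conclusion rests on the text alone and on reading section 8.1 to mean that the listed criteria decide entry. It needs no assumption about event rates. It has no effect on the target of about 125 enrolled and at least 100 completed subjects, or on the analysis of cell density.

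**What to change.** 1. In section 6.3.2.9 and the synopsis, drop the severity qualifier and exclude any known hypersensitivity to the active substance or another ingredient, matching label 4.2.
2. In both lists, add active ocular or periorbital infection as an exclusion, and add to section 8.1.2 that its absence is confirmed on Day 0 before the injection. A subject with infection is not entered and may be rescreened once it has resolved. Baseline assessments, and the pregnancy test where it applies, are repeated if they then fall outside the 7 days before first injection.
3. In section 7.2.2, state that the Appendix 1 contraindications also apply at Weeks 6 to 48. If infection is present, the dose is deferred within the existing 14-day window, or omitted with the reason recorded. Contact specular microscopy of an infected eye is postponed until resolution, since contact instruments are permitted (section 9.1.1). Study drug is stopped if hypersensitivity develops.

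The cost is four list edits (one rewording and one addition, each in two places), one line in the Day 0 list and a short dosing rule. In conduct, expect occasional screen failures and deferred or omitted doses; each omission loses one of nine injections. A postponed contact examination may also fall later than scheduled.
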